5.2 Volume of Blood Sampling

Total blood volumes required during study participation will be provided in the Informed Consent form provided to each patient. The Laboratory Manual will also describe unit and total blood volumes and provide examples based on various durations on study. Efforts will be made to limit PK and PD blood-letting during the study where on-going data analysis during the study suggests redundancy in sampling. Any such reductions in requirements for PK and PD blood sampling will be described and maintained in the Laboratory Manual.

BerGenBio ASA
[name]
[name]
Norway

5.3 Description of Study Interventions and Assessments

Details of the procedures to be followed for specified study assessments are provided. Additional assessments may be carried out as clinically indicated.

5.3.1 Demography and medical history

There will be a baseline assessment of demography (gender, race, ethnicity age (birth month and year), and medical history conducted at Screening to confirm eligibility and to record significant medical history, including smoking history, PD-(L)1 status on diagnosis (cohort B and C patients only) and concurrent illnesses in the CRF. Concurrent illnesses recorded at Screening (excluding the primary disease under evaluation), that worsen in severity or frequency from the time of signing the consent form, but before treatment allocation need to be reported as an adverse event if the event causes the patient to be excluded from the trial or is a result of a protocol specific intervention (Section 7.1).

5.3.2 Pregnancy and FSH test

Female patients of reproductive potential will have a pregnancy test carried out at Screening. This test must be carried out within 3 days prior to first study drug administration. A urine test is acceptable; however, a positive or equivocal urine test must be confirmed by a blood test. Patients confirmed as pregnant will be excluded from participation in the clinical study.

Female patients of reproductive potential will continue to have a pregnancy test before each cycle of pembrolizumab or at least monthly.

Female patients who require documented confirmation of post-menopausal status will have their FSH levels assessed at Screening. Where post-menopausal status is not confirmed, patients will be required to undergo pregnancy testing per protocol to confirm suitability to proceed to dosing.

5.3.3 ECOG performance score

ECOG PS will be assessed at the times given in Schedule of Study Assessments - [Table 4](#), [Table 5](#) and [Table 6](#). Details of the ECOG PS categories are presented in [Appendix A](#). Patients must be confirmed as ECOG PS 0 or 1 at Screening in order to be eligible for study participation.

5.3.4 Vital signs

Vital sign parameters will be taken at the times given in Schedule of Study Assessments - [Table 4](#), [Table 5](#) and [Table 6](#). The date and time of collection will be recorded in the source data and on the CRF.

Vital sign parameters will consist of measurements of temperature, resting heart rate, seated blood pressure and respiratory rate.

If any clinically significant findings are identified during the assessment of vital signs, the Investigator will record it as part of the medical history prior to start of dosing and as an AE post dose, where the finding represents a change from baseline. Findings identified prior to start of dosing must be checked against the study exclusion criteria (see [Section 3.2](#)).

BerGenBio ASA
[name]
[name]
Norway

5.3.5 Physical exam

A physical examination, including measurement of weight, will be taken at the times given in Schedule of Study Assessments - [Table 4](#), [Table 5](#) and [Table 6](#). The patient's height will be measured at Screening. The patient's weight will also be assessed at Screening and at the start of every cycle. Height and body weight will be obtained while the patient is wearing light clothing (without shoes).

A full physical examination will include assessment of the following categories: head, eyes, ears, nose, throat, heart, lungs, abdomen, skin, musculoskeletal, extremities, neurological, lymph nodes, and 'other'. After the Screening assessment, the physical examination may be reduced to a symptom-directed assessment.

If any clinically significant findings are identified during the physical examination, the Investigator will record it as part of the medical history prior to start of dosing and as an adverse event post dose, where the finding represents a change from baseline.

5.3.6 Clinical chemistry, hematology, coagulation and urinalysis

Blood and urine samples for determination of clinical chemistry, hematology, coagulation and urinalysis parameters will be taken at the times given in Schedule of Study Assessments – [Table 4](#), [Table 5](#) and [Table 6](#) and prior to administration of study treatment. The date and time of collection will be recorded in the source data and on the CRF.

All testing will be performed at each site's local laboratory. Coagulation parameters may be assessed from the hematology sample.

Copies of laboratory accreditation certificates and reference ranges will be obtained from each study site prior to the analysis of their first patient sample.

The laboratory variables to be measured are described in [Appendix E](#).

If any clinically significant findings are identified from the safety lab assessments, the Investigator will record it as part of the medical history prior to start of dosing and as an AE post dose, where the finding represents a change from baseline. Findings identified prior to start of dosing must be checked against the study inclusion and exclusion criteria ([Section 3.1](#) and [Section 3.2](#)).

5.3.7 Thyroid function test

Blood samples for thyroid function testing will be taken at the times given in Schedule of Study Assessment [Table 4](#), [Table 5](#) and [Table 6](#). The date and time of collection will be recorded in the source data and on the CRF.

The thyroid assessment panel should include:

- Triiodothyronine (T3) or Free Triiodothyronine (FT3)
- Free thyroxine (FT4)
- Thyroid stimulating hormone (TSH).

All testing will be performed at each site's local laboratory. This assessment may be performed from the clinical chemistry sample (see [Section 5.3.6](#)). Copies of laboratory accreditation

BerGenBio ASA
[name]
[name]
Norway

certificates and reference ranges will be obtained from each study site prior to the analysis of their first patient sample. Laboratory variables to be measured are described in [Appendix E](#).

If any clinically significant findings are identified, the Investigator will record it as part of the medical history prior to start of dosing and as an AE post dose, where the finding represents a change from baseline. Findings identified prior to start of dosing must be checked against the study inclusion criteria (see [Section 3.1](#)).

5.3.8 Echocardiography or MUGA

An echocardiography or MUGA assessment will be performed at Screening, and after every 6 months (every 8 cycles thereafter i.e., Cycle 9, Day 1; Cycle 17, Day 1; Cycle 25, day 1; Cycle 33, Day 1) until the end of 2 years.

Clinically significant findings identified prior to start of dosing must be checked against the study exclusion criteria ([Section 3.2](#)).

Patients who discontinue bemcentinib, but continue with monotherapy pembrolizumab, will stop undergoing an echocardiogram or MUGA assessment. Their final echocardiogram/MUGA assessment will occur if their next scheduled assessment is within the next 6 weeks (of discontinuing bemcentinib).

5.3.9 Electrocardiogram

A resting 12-lead ECG will be performed at the times given in Schedule of Study Assessments - [Table 4](#), [Table 5](#) and [Table 6](#). Each assessment time point must be performed in triplicate before starting treatment with bemcentinib.

All 12-lead ECGs should be recorded while the patient is in the supine position. ECGs will be recorded at 25 mm/sec. All efforts should be made to ensure that an identical ECG machine is used to collect traces for individual patients. The Investigator or designated physician will review the ECG results.

If any clinically significant findings are observed on the ECG, the Investigator will record it as part of the medical history prior to the start of dosing, and as an AE post dose where the finding represents a change from baseline. Clinically significant findings identified prior to start of dosing must be checked against the study exclusion criteria ([Section 3.2](#)).

Note that the average value of the three assessments performed at each time point should be applied, except at Screening, where both the Screening and pre-dose Cycle 1 Day 1 assessments should be combined. Patients may be excluded based on the initial triplicate assessment at Screening.

Patients who discontinue bemcentinib but continue with monotherapy pembrolizumab will stop undergoing an ECG.

Patients who have a bemcentinib interruption of for 14 days due to QTc prolongation or 12 weeks for immune-related toxicities (see [Table 12](#) and [Table 13](#)) will require an ECG twice weekly for the 2 weeks following recommencement of bemcentinib daily dosing. This is to ensure cardiac safety monitoring whilst bemcentinib returns to steady state.

BerGenBio ASA
[name]
[name]
Norway

5.3.10 Tumor Assessment Scans

Efficacy endpoints in this study, including ORR, DoR, PFS will all be based on tumor assessment scan evaluation by RECIST 1.1².

RECIST assessments will be performed at the times given in Schedule of Study Assessments - [Table 4](#), [Table 5](#), [Table 6](#) and [Table 7](#) using contrast-enhanced CT (preferred method) or MRI assessments of chest, abdomen, and pelvis. Additionally, x-ray and bone scans will be used as appropriate. Additional anatomy should be imaged based on signs and symptoms of individual patients at baseline and follow-up.

Baseline assessments should be performed no more than 28 days before start of study treatment, and ideally should be performed as close as possible to the start of study treatment. The Screening scan assessments must confirm the patient has measurable disease per RECIST 1.1² (see Inclusion Criteria [Section 3.1](#)).

For each patient, the same modality used at Screening must be used serially throughout the duration of study participation. All scan procedures will be performed according to standard local scan protocols to ensure consistency across study assessments.

All radiological and non-radiological (e.g., MRI) scans will be reviewed by the local site investigator; and if possible, stored electronically (de-identified with the patient's notes) at site.

A maximum of 5 target lesions, maximum of 2 per organ, must be selected at baseline. All target lesions are measurable. Target lesions should be selected on the basis of their size (longest diameter for non-nodal lesions or short axis for nodal lesions), but in addition should be those that lend themselves to reproducible repeated measurements. All remaining lesions present at baseline are considered non target, irrespective of whether they are measurable.

Disease assessments will be performed as per the schedule described in [Table 4](#) and [Table 5](#) – that is, every 9 weeks \pm 7 days for the first 46 weeks relative to the date of first treatment administration and then every 12 weeks \pm 7 days thereafter until confirmed objective disease progression as defined by RECIST 1.1² (irrespective of a delay to treatment or the reason for stopping treatment or subsequent therapy).

Any other sites at which new disease is suspected should also be adequately imaged at a follow-up visit.

If an unscheduled assessment is performed and the patient has not progressed, every attempt should be made to perform the subsequent assessments at their scheduled visits.

In addition to performing further scans where clinically indicated, scans also should be performed, as appropriate, to confirm response or disease progression.

5.3.11 Disease assessment

A disease assessment according to RECIST 1.1² will be performed and recording in the CRF whenever a tumor assessment scan is made during the Treatment period, Post Treatment Visit or during Follow Up Visits.

BerGenBio ASA
[name]
[name]
Norway

For more information on data evaluation by RECIST 1.1² for studies with checkpoint inhibitors, please refer to [Section 8.5](#).

5.3.12 Biomarkers

Evaluation of biomarkers will be performed at the time points described in Schedule of Study Assessments - [Table 4](#), [Table 5](#), [Table 6](#) and [Table 7](#).

Blood samples will be collected at these time points to prepare PMBC and blood samples for assessment of Axl inhibition and other relevant markers including sAxl such as MAPK signaling pathway intermediates (ERK/pERK), pAxl expression and T-cell populations, Akt, pAkt, SLFN11, Bcl2, and Puma.

Full details of the blood volumes required, plus requirements for sample collection, handling and shipment to the assigned central laboratory, will be described in Laboratory Manual for the study.

5.3.13 Tumor Sample Requirements

All patients are required to have a fresh (newly acquired) tumor biopsy. This can be taken up to 3 months before treatment starts provided the patient has not received any further chemotherapy or immunotherapy, or other anti-cancer therapy in the intervening period and that sufficient tumor tissue is available.

Tumor specimens are to be submitted in sufficient quantity to allow for PD-L1 immunohistochemistry (IHC) and Axl IHC analysis (see the Pathology Manual).

Samples with limited tumor content (<100 viable tumor cells), cytology, cell block, decalcified or formalin fixed but previously frozen, frozen sample, plastic embedded, bone, bone marrow, clot and fine needle aspirates are inadequate for defining tumor PD-L1 and Axl status.

Axl expression can only be obtained from a fresh (newly acquired) tumor tissue sample. PD-L1 expression can be determined from either a fresh (newly acquired) or archival sample. In all cases, the tumor tissue must not have been previously irradiated.

Different testing laboratories will be used for Axl kinase and PD-L1 expression.

The fresh (newly acquired) tumor tissue sample will be either newly obtained core needle biopsy (minimum gauge 18) or newly obtained excisional biopsy.

The following tumor tissue alternatives are available (all options require fresh tumor tissue sample; however, if there is insufficient fresh tumor tissue available, the 3rd option below allows the submission of archival tissue in addition to the fresh tissue sample):

- Where only a core needle biopsy is used, a minimum of 4 core (with 1-cm tumor in each core) biopsy samples are required. These should be placed in formalin and processed into 2 single paraffin embedded (FFPE) blocks (2 cores in one block and 2 cores in the other block) within 24-48 hours.
- Alternatively, where only a newly obtained excisional biopsy sample is used, this biopsy should be processed into 2 paraffin embedded (FFPE) blocks within 24-48 hours.
- Alternatively, 2 core (with 1-cm tumor in each core) needle (fresh tumor) biopsies or a single newly obtained excisional biopsy sample can be submitted (processed into one FFPE

BerGenBio ASA
[name]
[name]
Norway

block), together with either an archival (FFPE) tumor tissue block or a minimum of 10 unstained slides each 5 μ m cut from the archival tumor sample block.

If an archival tumor tissue block is to be sent, it is suggested that a minimum of 10 unstained slides each 5 μ m cut from the archival tumor sample block must be sent (rather than sending the whole archival block) and clearly labelled as having come from an archival block.

Optional 'on study' tumor tissue (fresh tissue) biopsies can be conducted on up to 2 separate occasions on suitable lesions (for example, lesions that have progressed). Separate patient consent is required for these 'on study' biopsies.

Full details of the requirements for both fresh and archival biopsy sample collection, handling and shipment to the assigned (central) laboratories, will be described in Pathology and Laboratory Manuals for the study.

5.3.14 Pharmacokinetics

Blood samples will be collected for the evaluation of the levels of bemcentinib and pembrolizumab in plasma at the time points described in Schedule of Study Assessments - [Table 4](#), [Table 5](#), [Table 6](#) and [Table 7](#).

Nominal PK blood sampling times should be adhered to as closely as possible. It is essential that the actual time and date of collection of each blood sample be recorded in the patient's records and in the CRF.

Full details of sample collection and handling for these samples will be described in Laboratory Manual for the study.

Full details of the blood volumes required, plus requirements for sample collection, handling and shipment to the assigned central laboratory, will be described in Laboratory Manual for the study.

BerGenBio ASA
[name]
[name]
Norway

6 STUDY MEDICATION AND ADMINISTRATION

Investigational Medical Product (IMP) will be provided by the Sponsor as summarized in **Table 10**. Both bemcentinib and pembrolizumab will be labelled in compliance with the Good Manufacturing Procedure (GMP) Annex 13 requirements or other applicable local regulatory guidelines.

Table 10: Product Descriptions

Product Name & Potency	Dosage Form
BGB324 [REDACTED]	HPMC capsule
MK-3475 10mL [REDACTED]	vial (liquid) Solution for Injection

6.1 Preparation and Dosing of Study Treatments

Further details on preparation and administration of both bemcentinib and pembrolizumab are provided in the Pharmacy Manuals.

6.1.1 Bemcentinib

Bemcentinib is provided in bottles containing a specified number of capsules per bottle to dispense to the patients. Patients will be asked to take the specified number of capsules for their prescribed dose on an empty stomach at a regular time each day with water. Patients should not eat for at least one hour following bemcentinib. Rescue treatment with antacids, proton pump inhibitors and histamine receptor 2 inhibitors can be initiated, provided they are taken in the evening. On pembrolizumab dosing days, patients will be asked not to take their bemcentinib dose before coming into the clinic. On these days, pembrolizumab will be administered first, and the patient observed for 1 hour after the end of infusion (for infusion and other AEs), prior to taking their bemcentinib dose (on an empty stomach and with water).

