- 24. Existing gastrointestinal disease affecting drug absorption such as celiac disease or Crohn's disease, or previous bowel resection which is considered to be clinically significant or could interfere with absorption.
- 25. Known lactose intolerance.
- 26. Requires vitamin K antagonists. Note: Patients receiving low doses prescribed to maintain the patency of venous access devices may be included. Note: Factor Xa antagonists are permitted.
- 27. Treatment with any of the following: histamine receptor 2 inhibitors, proton pump inhibitors or antacids within 7 days of start of study treatment.
- 28. Treatment with any medication which is predominantly metabolized by CYP3A4 and has a narrow therapeutic index.
- 29. Known severe hypersensitivity (\geq Grade 3) to bemcentinib, pembrolizumab, and/or any of their excipients.
- 30. Any evidence of severe or uncontrolled systemic conditions (e.g., severe hepatic impairment) or current unstable or uncompensated respiratory or cardiac conditions, or ongoing.
- 31. Has active infection requiring systemic therapy (apart from cutaneous infections).
- 32. Has received radiation to the lung of >30 Gy within 6 months of first dose.
- 33. Has a history or current evidence of any condition, therapy, or laboratory abnormality that might confound the results of the trial, interfere with the patient's participation for the full duration of the trial, or means it is not in the best interest of the patient to participate, in the opinion of the Investigator.
- 34. Is pregnant or breastfeeding, or expecting to conceive or father children within the projected duration of the trial, starting from Screening through to 120 days after the last dose of study treatment.
- 35. Has known psychiatric or substance abuse disorders that would interfere with cooperation with the requirements of the trial.
- 36. Cohorts B and C: Has an EGFR mutation or ALK genomic rearrangement.
- 37. Has received an allogeneic tissue/solid organ transplant.

BerGenBio ASA
[name]
[name]
Norway

Statistical Methods and Sample Size

Evaluable for safety (ES): An evaluable patient will have received at least one combination dose.

Evaluable for efficacy (EE): An evaluable for safety (ES) patient who has at least one on -treatment scan as per protocol schedule.

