8 Fresh tumor tissue taken within 3 months of first dose (provided the patient has not received any further chemotherapy or immunotherapy, or other anti-cancer therapy in the intervening period and that sufficient tumor tissue is available) from all patients at Screening is mandatory, and optional at up to 2 time points during participation in the clinical trial ('on-study' biopsy). Where possible, these optional samples should be taken at the point of tumor response or progression. Suitable archival biopsy material may also be obtained at Screening. Please refer to protocol [Section 5.3.13](#), the Laboratory or Pathology Manual for full details on biopsy sample collection, time-points, processing, storage and shipment. If a patient discontinues bemcentinib (but continues pembrolizumab), there is no requirement for the optional 'on study' biopsy.

9 Blood samples will be collected at Screening (or D1 pre-dose), D4, D8, then at every study visit up to and including C9 D1 to prepare PBMC and serum samples for relevant Axl signaling and inhibition biomarker assessment. Please refer to the Laboratory Manual for full details on biomarker sample collection, time-points, processing, storage and shipment.

10 Pembrolizumab dose of 200 mg will be administered every 3 weeks (timing window +/- 3 days). Each dose will be infused over 30 minutes (timing window -5/+10 minutes)

11 Bemcentinib will be taken orally once daily. On visits when pembrolizumab and bemcentinib are given on the same day, pembrolizumab must be given first and the patient observed for 1 h prior to administration of bemcentinib.

12 a) The maximum PK sampling time points for the measurement of bemcentinib in blood will be: C1 D1 pre-dose, 2, 4, 6, 8 hours; D2 pre-dose; D3 pre-dose, 2, 4, 6, 8 hours; D4 pre-dose; and then pre-dose at C1D8, C1D15, C2D1 and then C3D1. Samples should be taken contemporaneously with the ECG assessments on C1 D1-4. All sample times are approximate, but every effort must be made to take PK samples at specified times.

BerGenBio ASA
[name]
[name]
Norway

b) The maximum PK sampling time points for the measurement of pembrolizumab in blood will be: C1 D1 pre-dose; D2; D3; D4; and then at C1D8, C1D15, C2D1 pre-pembro dose and then C3D1 pre-pembro dose. All sample times are approximate but every effort must be made to take PK samples at specified times

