Systemic exposure from Formulation 1 in Study BGBC003 is markedly lower than that from Formulation 2 in Study BGBC004. Furthermore, systemic exposure from Formulation 1 is lower than that from Formulation 2 in Study BGBC003. Between-patient variability in systemic exposure to bemcentinib appeared to be lower after administration of Formulation 2 (in study BGBC004) compared to Formulation 1. The lower variability may be associated with enhanced solubility of bemcentinib in Formulation 2, a formulated product with solubilisers and particle size considerations. This will enable a product with a dissolution profile suitable for oral administration intended for immediate release in the stomach in the fasted state. The difference in systemic exposure between the two formulations could also have occurred as a result of administering bemcentinib in the fed or fasted state. For Study BGBC008 the starting dose will be 400 mg loading dose on Days 1, 2 and 3, followed by a daily maintenance dose of 200 mg. Bemcentinib will be administered on an empty stomach, at approximately the same time each day; antacids are not used for at least 2 hours after intake of bemcentinib (see IB for details).

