16. Has a diagnosis of immunodeficiency or is receiving systemic steroid therapy or any other form of immunosuppressive therapy within 7 days prior to the first dose of study treatment. *Note: The use of physiologic doses of corticosteroids may be approved after consultation with the Sponsor.*
17. Active autoimmune disease that has required systemic treatment in past 2 years (i.e., with use of disease modifying agents, corticosteroids, or immunosuppressive drugs).

BerGenBio ASA
[name]
[name]
Norway

Note: Replacement therapy (e.g., thyroxine, insulin, or physiologic corticosteroid replacement therapy for adrenal or pituitary insufficiency, etc.) is not considered a form of systemic treatment.

18. Known history of human immunodeficiency virus (HIV) (HIV 1/2 antibodies).
19. Has known active infection with Hepatitis B (e.g., HBsAg reactive) or Hepatitis C (e.g., HCV RNA [qualitative] is detected). *Note: i) Patients with a history of hepatitis B infection are eligible provided they are hepatitis B surface antigen negative ii) Patients with a history of hepatitis C infection are eligible provided they have no evidence of hepatitis C RNA using a qPCR at least 6 months after completing treatment for hepatitis infection.*
20. Has received a live-virus vaccination within 30 days of planned treatment start. *Note: Seasonal flu vaccines that do not contain live virus are permitted.*
21. Has a history of (non-infectious) pneumonitis that required steroids or current pneumonitis.
22. Has a history of interstitial lung disease.
23. Inability to swallow or tolerate oral medication.
24. Existing gastrointestinal disease affecting drug absorption such as celiac disease or Crohn's disease, or previous bowel resection which is considered to be clinically significant or could interfere with absorption.
25. Known lactose intolerance.
26. Requires vitamin K antagonists. *Note: Patients receiving low doses prescribed to maintain the patency of venous access devices may be included. Note: Factor Xa antagonists are permitted.*
27. Treatment with any of the following: histamine receptor 2 inhibitors, proton pump inhibitors or antacids within 7 days of start of study.
28. Treatment with any medication which is predominantly metabolized by CYP3A4 and has a narrow therapeutic index.
29. Known severe hypersensitivity (\geq Grade 3) to bemcentinib, pembrolizumab, and/or any of their excipients.

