6.8 Permitted and Restricted Concomitant Medications

In general, medications or vaccinations specifically prohibited in the exclusion criteria are not allowed during the ongoing trial. Treatment with antacids, proton pump inhibitors and histamine receptor 2 inhibitors can be initiated as rescue therapy after patients have been receiving bemcentinib for one week, provided they are taken in the evening.

If there is a clinical indication for any medication or vaccination specifically prohibited during the trial, discontinuation from trial therapy or vaccination may be required. The investigator should discuss any questions regarding this with the Sponsor Clinical Director. The final decision on any supportive therapy or vaccination rests with the investigator and/or the patient's primary physician. However, the decision to continue the patient on trial therapy or vaccination schedule requires the mutual agreement of the investigator, the Sponsor and the patient.

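### Sections 6.1.1 and 6.8 disagree on when acid-reducing rescue may start, and 7 of the 16 scheduled bemcentinib PK samples, including the whole Day 3 profile, depend on which section a site follows

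*Combined protocol and SAP*

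**What the plan says.** Four places in the protocol deal with antacids, proton pump inhibitors (PPIs) and histamine receptor 2 (H2) inhibitors.

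- **Section 6.1.1**, on how bemcentinib is taken: "Rescue treatment with antacids, proton pump inhibitors and histamine receptor 2 inhibitors can be initiated, provided they are taken in the evening". Evening intake is the only condition. The same section has patients take bemcentinib "on an empty stomach at a regular time each day with water".
- **Section 6.8**, on concomitant medication, begins from the general position that "medications or vaccinations specifically prohibited in the exclusion criteria are not allowed during the ongoing trial". It then makes an exception for the same three drug classes, which "can be initiated as rescue therapy after patients have been receiving bemcentinib for one week, provided they are taken in the evening".
- **Section 1.5**, the dose rationale, says that "antacids are not used for at least 2 hours after intake of bemcentinib" and refers to the Investigator's Brochure. It does not mention PPIs or H2 inhibitors.
- **Exclusion criterion 27** bars these drugs. The synopsis words it as "histamine receptor 2 inhibitors, proton pump inhibitors or antacids within 7 days of start of study treatment"; Section 3.2 ends the same phrase at the start of the study and leaves out the word for treatment.

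Bemcentinib Cmax, AUC and half-life are a named secondary endpoint (Section 2). Sections 8.4 and 8.12.3 define the PK subset and parameters without a rule for acid-reducing co-medication. Section 8.12.3 assigns the PK analysis plan to the SAP. Section 6.9 has all concomitant medication recorded on the CRF.

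**The concern.** Section 6.1.1 is where site staff look for dosing instructions, and it does not refer to 6.8. One site could follow it and allow rescue in the first week. Another could follow 6.8 and refuse it. Each could point to the protocol. That week holds all the serial bemcentinib sampling.

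The protocol treats stomach conditions as relevant to exposure. It describes the current formulation as designed for release in the fasted stomach, names food as a possible reason for exposure differences (Section 1.5), and bars acid reducers at entry. If acid suppression changes absorption, a pooled summary of Cmax and AUC would combine two conditions in proportions set by which section each site happened to read.

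**Working it through.** The plan states no figure on this point, so there is none to reproduce. The check sets the rules side by side and then applies them to the sampling schedule.

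**Step 1. The rules**

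| Place | Drugs | Earliest on-study start | Timing condition |
|---|---|---|---|
| 6.1.1 | Antacids, PPIs, H2 inhibitors | Not stated | Evening |
| 6.8 | Same | After one week on bemcentinib | Evening |
| 1.5 | Antacids only | Not stated | Not in the 2 hours after a dose |
| Exclusion 27 | All three | Entry criterion: 7 days | Anchored to start of treatment (synopsis) or start of study (3.2) |

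Screening lasts up to 28 days, so the two anchors for exclusion 27 can lie up to 28 days apart if start of study is read as the patient's entry to screening.

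**Step 2. The samples.** Footnote 12a to the assessment schedules gives "C1 D1 pre-dose, 2, 4, 6, 8 hours; D2 pre-dose; D3 pre-dose, 2, 4, 6, 8 hours; D4 pre-dose", followed by single pre-dose samples at C1D8, C1D15, C2D1 and C3D1.

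- Total: 5 + 1 + 5 + 1 + 1 + 1 + 1 + 1 = 16.
- Days 1 to 4: 5 + 1 + 5 + 1 = 12, and 12/16 = 75%.

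**Step 3. Which Day 1 to 4 samples can follow on-study rescue?**

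- Under 6.8: none of the 12.
- Under 6.1.1 alone, the earliest rescue is the evening of Day 1. The Day 2 pre-dose sample can follow one evening of rescue, the five Day 3 samples up to two, and the Day 4 pre-dose sample up to three.
- Count: 1 + 5 + 1 = 7. As shares, 7/12 = 58% and 7/16 = 44%.

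**Step 4. The Day 1 samples from 0 to 8 hours.** The documents do not define evening; assume that it begins at 18:00.

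- 18:00 minus 8 h = 10:00. A dose at or before 10:00 has its 8 h sample no later than the start of evening.
- 18:00 minus 6 h = 12:00. A dose between 10:00 and 12:00 has only its 8 h sample in the evening.
- With evening from 17:00, both limits move one hour earlier, to 09:00 and 11:00.

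So evening rescue can reach only the tail of this profile when dosing is in the morning. Section 1.5 read alone would let an antacid, but not a PPI or H2 inhibitor, into the window from 2 hours after the dose.

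**Step 5. The parameters.** Table 22 defines AUC over 0 to 24 hours, so the Day 2 and Day 4 pre-dose samples close the Day 1 and Day 3 profiles. Under 6.1.1 alone:

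- Day 3 Cmax, and all 5 + 1 = 6 points of the Day 3 AUC, can follow rescue.
- The Day 1 AUC is exposed mainly at its last point. That concentration comes from a dose taken before the rescue, so it is the least sensitive of the seven.

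**Step 6. Later samples.** C1D15, C2D1 and C3D1 can be taken under rescue by either section, so the conflict does not cause that. C1D8 is borderline: it depends on whether one week is counted to the evening of Day 7 or Day 8. It is left out of the seven; with it the count would be 8/16 = 50%.

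**The case against.** The best defence is that the passages can all be obeyed together. Rescue started after one week, taken in the evening and more than 2 hours after the dose satisfies 6.1.1, 6.8 and 1.5. Section 6.8 is the dedicated and more specific section. The sentence in 1.5 is a restriction in a rationale section, not a permission. A site that reads everything has one answer. This stands against calling the rules mutually incompatible. It does not remove the problem, because 6.1.1 permits on its face what 6.8 forbids in week 1 and gives no cross-reference.

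Several stronger readings are tempting, and the documents do not support them.

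- **That 6.1.1 expressly allows rescue from Day 1.** It is silent on the start. The evening of Day 1 is the earliest time that its silence leaves open.
- **That both full profiles, or 75% of the samples, are compromised.** The 12 of 16 counts samples in the first week. It includes the Day 1 pre-dose sample and Day 1 post-dose samples that evening rescue largely cannot reach.
- **That the evening condition fails because a patient may dose in the evening.** Days 1 to 4 are clinic visits and Days 1 and 3 need samples to 8 hours, so evening dosing is implausible on profile days.
- **That the PK plan lacks a handling rule by oversight.** Sections 8.3 and 8.12.3 leave such rules to the SAP, and affected samples can be identified from recorded medication. The request is that the SAP contain the rule.
- **That exposure is biased.** Section 1.5 does not say that acid suppression changes bemcentinib exposure.

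**Conclusion.** The point holds as an inconsistency with a bounded consequence. Sections 6.1.1 and 6.8 set different conditions for the same drugs, 1.5 adds another for antacids, and exclusion 27 has two anchors. Seven of the 16 scheduled bemcentinib samples (44%) can follow acid-reducing rescue under 6.1.1 read alone and cannot under 6.8. They include the whole Day 3 profile, one of only two serial profiles and the only one after repeated loading doses.

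This rests on three assumptions: some sites work from 6.1.1 without 6.8; patients enter free of acid reducers at first dose, which is clear only with the synopsis wording of exclusion 27; and dosing on profile days is in the morning.

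The count shows which samples can be affected, not how many will be or by how much. The documents give neither the expected frequency of rescue nor the size of any effect. Only the secondary PK endpoint is concerned. Response rate, the Simon boundaries and the stopping decisions are untouched. The point should be corrected, but it is not critical.

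**What to change.** - **Protocol.** Reconcile Sections 1.5, 6.1.1 and 6.8 so that they state the same conditions, and give exclusion 27 one anchor in the synopsis and in Section 3.2. Which clinical rule applies is for the sponsor to decide.
- **SAP, PK section.** Flag each bemcentinib concentration taken while a recorded acid reducer is in use. Present the Cmax and AUC summaries with and without the flagged data. Which set leads is a matter of preference, provided that it is stated in advance.

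The cost is one text correction and one additional PK summary. No new data are needed, because concomitant medication is already collected. If patients have been treated under the present wording, the flag also shows whether any first-week rescue took place.
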